8.3.5. Pregnancy testing for participants of childbearing potential

- Participants of childbearing potential (POCBP) must perform a pregnancy test before the administration of any dose of study intervention. Pregnancy testing must be done even if the participant is menstruating at the time of the study visit. The study intervention may only be administered if the pregnancy test is negative.
- Serum samples will be sent for pregnancy testing for the Screening Visit and all other timepoints. At the Day 1 Visit (before start of study treatment), a urine test must be used to confirm pregnancy status prior to administration of study treatment.

Additionally at the Day 1 Visit, a serum sample will be sent for pregnancy testing at the same time.

- Refer to Section 8.4.5 for the information on study continuation for participants who become pregnant during the study.

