1.2. Study design schematic

1.3. Schedule of activities (SoA)

The schedule of study visits and expected study procedures and activities are detailed in [Table 1](#) (Screening Period, Monotherapy Period) and [Table 2](#) (Open Label Follow-up Period and Early Discontinuation Visit).

While unlikely, the timing of assessments in Part 2 may be adjusted based on the interim analyses of the PK and/or antiviral results to ensure appropriate monitoring (e.g., to obtain data closer to the time of peak plasma concentrations or to maximal viral load decline). Any non-safety driven changes in the timing of the planned study assessments will be documented and communicated to investigators but will not constitute a protocol amendment.

Any emerging safety issues that constitute a substantial amendment and require alteration of the safety monitoring scheme or amendment of the ICF will be approved by appropriate regulatory agencies and IECs/IRBs before implementation.

Table 1 Schedule of activities - screening and monotherapy period

Clinical Procedures	Screening ¹	Monotherapy Treatment Period, Capsid Inhibitor (Double Blind) Day 1→Day 10					
	Visit 1	Visit 2	Visit 3	Visit 4	Visit 5	Visit 6	Visit 7
	Approximately 7 to 14 days before Day 1	Day 1 Fixed visit. No window.	Day 2 Fixed visit. No window.	Day 3, 4 or 5 Conduct visit on Day 3, 4 or 5	Day 6 Fixed visit. No window.	Day 7 Fixed visit. No window.	Day 8, 9 or 10 Conduct visit on Day 8, 9 or 10
Outpatient clinic visit ²	X	X	X	X	X	X	X
Informed consent	X						
Demography	X						
Inclusion / exclusion criteria	X	X					
Medical history, CDC classification	X	X					
Prior anti-retroviral therapy	X	X					
HIV-1 RNA	X	X	X	X	X	X	X
HIV-1 capsid genotype/phenotype		X	X	X	X	X	X
Lymphocyte T-cell subsets (CD4, CD8)	X	X					
Hepatitis B and C serologies	X						
SARS CoV-2 point of care test		X					
Physical exam ³	X	X			X		
Height, weight, BMI	X						
Vital signs	X	X	X	X	X	X	X
C-SSRS administration (Baseline form)	X		X		X		
12-lead ECG	X	X	X				X
Safety labs (hematology, chemistry, urinalysis) ⁴	X	X	X	X	X	X	X
Serum pregnancy (urine also on Day 1) for POCBP	X	X					
Plasma PK sampling ⁵		X	X	X	X	X	X

Clinical Procedures	Screening ¹	Monotherapy Treatment Period, Capsid Inhibitor (Double Blind) Day 1→Day 10					
	Visit 1	Visit 2	Visit 3	Visit 4	Visit 5	Visit 6	Visit 7

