7. The assessment of HIV-associated conditions and AEs/SAEs is conducted throughout the study. SAEs are assessed from the time of consent. Non-serious AEs are assessed from the time of first dose. CCI [REDACTED]

Table 2 Schedule of activities – follow-up period with open label standard of care and early discontinuation visit

Clinical Procedures	Follow-Up Phase					Early Discontinuation ⁶
	Visit 8	Visit 9	Visit 10	Visit 11	Visit 12 ⁵	
	Day 11 Fixed visit. No window.	Day 18 +/- 3 day window.	Day 25 +/- 3 day window	Day 32 +/- 3 day window	Day 39 +/- 3 day window	
Outpatient clinic visit	X	X	X	X	X	X
HIV-1 RNA	X Primary endpoint timepoint	X	X	X	X	X
HIV-1 capsid genotype/phenotype	X	X	X	X	X	X
Lymphocyte T-cell subsets (CD4, CD8)	X				X	X
Physical exam ²					X	X
Height, weight, BMI	X				X	X
Vital signs	X	X	X	X	X	X
C-SSRS administration (Since Last Visit form)	X				X	X
12-lead ECG	X	X	X	X	X	X
Safety labs (hematology, chemistry, urinalysis) ³	X	X	X	X	X	X
Serum pregnancy	X	X	X	X	X	X
Plasma PK single sample	X	X	X	X	X	X
Plasma for storage	X	X	X	X	X	X
AE/SAE assessment	X	X	X	X	X	X
HIV-associated conditions	X	X	X	X	X	X
Concomitant medication review	X	X	X	X	X	X
Standard of care cART ¹	X	X	X	X	X	X

1. Standard of care cART will be chosen by the investigator and first dose will be directly observed at the end of the Day 11 visit. Choice of cART will be informed by local treatment guidelines, accessibility and locally run genotypic/phenotypic results (if available).
2. Complete Physical Exam performed at Screening and Day 39/Early Discontinuation. A symptom directed physical exam will be performed at all other noted visits. Any abnormalities to be recorded as AEs.
3. See Section 10.2 for details of clinical laboratory tests. Fasting bloodwork for the lipid panel is required at Days 1, 6, 11, 25, 39/Early Discontinuation.

CONFIDENTIAL

218307
Protocol Final

4. Plasma samples for storage will be collected at each visit, including unscheduled visits. These samples will be used when needed, such as when samples are lost or where quantity is insufficient for testing. In the event samples are not used by study completion and consent is obtained for further research, then the stored samples may be utilized for additional research on antiretroviral resistance and/or HIV-1 disease biology/host immune response (excluding any human genetic testing).

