• Maximum change from baseline (Day 1) in plasma HIV-1 ribonucleic acid (RNA) through Day 11.	Overtly healthy (other than HIV-1 infection) treatment naïve individuals	VH4004280 or placebo single dose on Day 1 or VH4011499 or placebo single dose on Day 1 and Day 6	Mean of maximum change from Baseline in log10 HIV-1 RNA during Days 1-11	
Discontinuation of study treatment due to any reason: Treatment policy strategy, i.e., any HIV-1 RNA data available after study treatment discontinuation day + 1 and prior to starting SOC will be used in calculation of max VLD
 
Use of SOC medication prior to Day 11: While on-treatment strategy, i.e., HIV-1 RNA collected after initiation of SoC, if for any reason this takes place prior to Day 11 will be excluded from calculation of max VLD
 
Use of prohibited medication: Treatment policy strategy, i.e., any HIV-1 RNA data available after use of prohibited medication will be used in calculation of max VLD
 
Missed or partial doses of study treatment: Treatment policy strategy, i.e., HIV-1 RNA collected after missed or partial dose(s) will be used in calculation of max VLD
 
Rationale: Interest is in evaluating efficacy irrespective of study treatment discontinuation or missed/partial doses, or use of prohibited medications, hence a treatment policy strategy is appropriate. Also, interest is to evaluate efficacy of VH4004280/VH4011499 monotherapy and not in combination with other antiretroviral medication hence a while on-treatment strategy is appropriate.
 
Note: discontinuation or missed or partial doses of VH4004280 is not possible as only a single dose on Day 1 is administered, hence these IEs apply only to VH4011499 and to placebo matched for VH4011499.

Secondary Objective: To assess the safety and tolerability of orally administered VH4004280 and VH4011499				

Endpoints	Estimand			
	Population	Treatment	Summary Measure	Intercurrent event (IE) / strategy / rationale

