5.3. Lifestyle considerations**5.3.1. ~~CCI~~ and dietary restrictions**

Participants will be required to fast for at least 8 hours (overnight) prior to the morning check-in for the Days 1, 6, 11, 25, and 39/Early Discontinuation Visits. Blood work for the safety labs and HIV-1 RNA will be drawn at the beginning of any clinic visit and, when applicable, before consumption of any ~~CCI~~ and dosing.

~~CCI~~

Refrain from excessive consumption of red wine, Seville oranges, grapefruit or grapefruit juice, pomelos, exotic citrus fruits, grapefruit hybrids, or fruit juices from 3 days prior to the first dose of study medication through the Day 11 visit. Excessive consumption is defined as more than one glass of red wine or juice or one fruit per day, in combination.

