1.2. Study Design

Overview of Study Design and Key Features	
	
Design Features	
 Phase IIa, PoC, multi-center, randomized, double-blind (sponsor unblinded), placebo-controlled (by each capsid inhibitor) study Orally administered VH4004280 and VH4011499 monotherapy over 10 days in ART naive HIV-1 viremic adults The study will evaluate the antiviral effect, safety, tolerability and PK/PD of VH4004280 and VH4011499 Participants have a Screening visit approximately 7 to 14 days prior to first dose on Day 1 On Day 1 randomized participants enter a monotherapy phase of 10 days (i.e. up to Day 11) On Day 11, after collection of HIV-1 RNA sample, participants will start open-label SoC combination ART CCI Total duration of study participation is approximately 45 to 66 days based on the following: 
 7 to 14 days, with a maximum of 28 days permitted in some cases for screening/qualification period, 10 days for treatment with the study intervention (monotherapy period) and 28 days for follow up visits (Follow-Up period)
Study intervention	
 A single dose of orally administered VH4004280 or matched placebo for VH4004280 on Day 1 or

Overview of Study Design and Key Features	
	
 • A single dose of orally administered VH4011499 or matched placebo for VH4011499 on Days 1 and 6
Study intervention Assignment	
 • Part 1a: 100mg VH4004280, 300mg VH4004280 or placebo in a 6:6:2 ratio • Part 2a (if conducted): 50-600mg VH4004280 (exact dose to be decided after first Interim) or placebo in a 6:1 ratio • Part 1b: 25mg VH4011499, 100mg VH4011499 or placebo in a 6:6:2 ratio • Part 2b (if conducted): 100mg on Day 1 to 250mg on Days 1 & 6 VH4011499 (exact dose to be decided after second Interim) or placebo in a 6:1 ratio
Interim Analysis	
 • A first informal interim analysis will be conducted after 9 participants (i.e., 4 participants per active arm and 1 placebo participant) from Part 1a have completed their Day 11 visit. • A second informal interim analysis will be conducted after 9 participants (i.e., 4 participants per active arm and 1 placebo participant) from Part 1b have completed their Day 11 visit. • Conduct of parts 2a and 2b depend on results of first and second interim analysis, respectively

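### Exclusion 28 contradicts its own hepatitis B algorithm, and Section 8.3.5 does not match the pregnancy-test schedule around the Day 6 VH4011499 dose; the male contraception wording also conflicts

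*Protocol*

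**What the plan says.** **Hepatitis B (Protocol 5.2, exclusion 28).** The lead line makes either HBsAg or core antibody at screening exclusionary. The bullets beneath send HBsAg-negative people through an algorithm. Those positive for anti-HBc and anti-HBs count as immune and stay eligible. Those positive for anti-HBc, negative for anti-HBs and positive for HBV DNA are excluded. HBV DNA is run only for people who are anti-HBc positive and negative for both HBsAg and anti-HBs. SAP 3.1, Table 2, criterion 07 removes from the per-protocol (PP) set anyone who met an exclusion criterion.

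**Pregnancy testing.** Protocol 8.3.5 says participants of childbearing potential "must perform a pregnancy test before the administration of any dose of study intervention" and allows dosing only on a negative result. The Table 1 row, "Serum pregnancy (urine also on Day 1) for POCBP", is marked at Screening and Day 1 only. Table 2 resumes the "Serum pregnancy" row at Day 11. Section 8.4.5 makes dosing conditional on the Screening blood test and the Day 1 urine test and leaves later testing to the schedule. The estimand table in Protocol 3 gives the regimen as "VH4011499 or placebo single dose on Day 1 and Day 6". Sections 7.1.3 and 8.4.5 stop further dosing once a participant is pregnant.

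**Male contraception.** Inclusion 7 sets no requirement for participants who were male at birth. Section 10.4.2.2 makes condom use, plus a highly effective method for a partner of childbearing potential, mandatory.

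**The concern.** Each pair of texts gives a site two rules for the same decision.

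For hepatitis B, a site that stops at the lead line turns away people the algorithm accepts, while a site that follows the algorithm enrols people who literally meet an exclusion criterion. Protocol 5 forbids eligibility waivers, so a site cannot settle this by exception. Criterion 07 then carries the ambiguity into PP membership.

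For pregnancy testing, a site that follows Table 1 exactly gives the Day 6 dose without a fresh test, which 8.3.5 read literally would not allow. In the two-dose regimen, Day 6 is the only dose the stop-dosing rule can prevent. Section 10.2 permits extra tests at any time, but nothing in the schedule prompts one.

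The male contraception conflict affects consent and counselling but no endpoint or analysis.

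**Working it through.** The plan gives no figure to reproduce on this point. The check sets the texts side by side, with short arithmetic for size.

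**Exclusion 28, by serology profile**

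| HBsAg | anti-HBc | anti-HBs | HBV DNA | Lead line | Algorithm | Agree? |
|---|---|---|---|---|---|---|
| + | any | any | not needed | excluded | excluded | yes |
| − | + | + | not run | excluded | expressly kept | no |
| − | + | − | − | excluded | not named as excluded | no, by implication |
| − | + | − | + | excluded | excluded | yes |
| − | − | any | not run | kept | kept | yes |

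Of the three HBsAg-negative, anti-HBc-positive profiles, one conflicts expressly, one by implication, and one agrees. The implied conflict rests on two facts: DNA testing is ordered for isolated anti-HBc, and only a positive DNA result is named as excluding.

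**Reach into the analyses.** SAP 4.2.3 repeats the primary analysis on the PP set, and SAP 4.2.4.1 runs the by-visit change-from-baseline summaries and the plot of means with 95% CIs on it too. SAP 4.2.2 bases the primary analysis on the FAS, which does not depend on eligibility deviations.

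Size if one participant in a six-person arm were dropped (t-based 95% CI half-width, in SD units):

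- n = 6: 2.571/√6 = 1.049
- n = 5: 2.776/√5 = 1.242
- Ratio: 1.242/1.049 = 1.18, so 18% wider at the same SD

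**Pregnancy tests against doses (VH4011499 or its placebo)**

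- Scheduled tests: Screening, Day 1 (serum and urine), then Day 11, 18, 25, 32 and 39.
- Doses: Day 1 and Day 6.
- Tests after Day 1 and up to the Day 6 dose: 0.
- Day 1 test to second dose: 6 − 1 = 5 days. Between scheduled tests: 11 − 1 = 10 days.

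The Day 6 column is not blank for other procedures; physical examination, for one, is marked there.

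**Participants concerned.** Part 1b plans 6 + 6 + 2 = 14, of whom 12 receive active drug. Part 2b plans 6 + 1 = 7. SAP 1.2 gives its range as "Part 2b (if conducted): 100mg on Day 1 to 250mg on Days 1 & 6 VH4011499", so it may or may not include a Day 6 dose. The documents do not say how many will be of childbearing potential. The range is therefore 0 to 14, or 0 to 21 if Part 2b is dosed on Day 6, before any replacements under Sections 7.1 and 7.2. VH4004280 is a single Day 1 dose and is not involved.

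**The case against.** **Exclusion 28.** The text tells sites to exclude according to the algorithm, so the specific rule arguably governs. The risk table in 2.3.1 speaks of HBV coinfection, and Section 10.2 lists HBV DNA only if indicated; both fit the algorithm. This stands as evidence of intent. It does not make the lead line correct, and criterion 07 refers to the criteria without saying which part of one controls. The 18% is conditional: someone enrolled under the algorithm must later be classed under the lead line and pass uncorrected through the deviation review before unblinding (SAP 6.1.3). A CI for mean maximum viral load decline is also optional under SAP 4.1.1.

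**Pregnancy testing.** A reader might infer that a Day 6 test was intended and then left out of Table 1. The documents do not support that. Section 8.4.5 and Table 1 agree with each other, and the wording in 8.3.5 can mean before any drug is given at all. Testing before the first dose is the likelier intent. On the other side, 8.4.5 and the risk table refer to the first dose explicitly where they mean it, so the broader wording in 8.3.5 is not obviously shorthand. What stands is an inconsistency between sections.

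A reader might also infer that the stop-dosing rule has nothing to act on by Day 6. That goes too far. A serum sample is sent on Day 1 alongside the urine test, and a result returned after the first dose could still stop the second. Unscheduled tests are allowed too.

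**Male contraception.** The risk table and 8.4.5 place birth control on participants of childbearing potential only, which might suggest deleting 10.4.2.2. The documents do not show which text is the mistake, and removing a protective rule needs the toxicology data.

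**Conclusion.** The point holds as three textual contradictions.

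1. Exclusion 28 is wrong as written and is the clearest of the three. Its intent can be recovered from the algorithm. The exposure is limited to the PP sensitivity analysis and the PP versions of the by-visit summaries. It would be 18% on a CI width if one of six were lost, and nothing if the deviation review applies the algorithm. The documents give no prevalence for the affected profiles, so the chance of this cannot be stated.
2. Section 8.3.5 is inconsistent with 8.4.5 and Table 1 for 0 to 14 planned participants (0 to 21 with a Day 6 dose in Part 2b). The expected harm is small: Screening and Day 1 tests must be negative, contraception is required through Day 39, and the risk table reports no embryo-fetal effects of VH4011499 in rats or rabbits at the doses it cites. A Day 6 test would add a small safety margin against early undetected pregnancy, a risk the protocol itself names. The documents give no detection rate to size that gain.
3. Inclusion 7 and 10.4.2.2 contradict each other. This is minor.

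None of the three touches the FAS primary analysis or the sample size. They should be fixed because the instructions conflict and the correction is cheap.

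**What to change.** 1. Reword the exclusion 28 lead line to *Evidence of HBV infection as defined by the algorithm below*. If it is intended, add a line saying that isolated anti-HBc with negative HBV DNA is not excluded.
2. Choose one pregnancy-testing rule:
   - Preferred: add a pre-dose urine test for participants of childbearing potential on Day 6 in arms dosed that day. Mark it in Table 1 and make 8.4.5 require a negative pre-dose test for each dose. Amend the 8.3.5 sentence "Serum samples will be sent for pregnancy testing for the Screening Visit and all other timepoints" so that urine may be used on Day 6.
   - Alternative, if testing only before the first dose is intended: change 8.3.5 to *before the first dose*. This removes the inconsistency but adds no test before the Day 6 dose.
3. Ask the sponsor to reconcile Inclusion 7 with 10.4.2.2 from its toxicology data, with neither text deleted by default.

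Cost: the preferred option adds one urine test per affected participant at a visit that already exists ("Day 6 Fixed visit. No window"). Samples are already taken before dosing there: "Blood work for the safety labs and HIV-1 RNA will be drawn at the beginning of any clinic visit". The rest is wording in the protocol and any matching consent text. Sample size and SAP do not change.

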8.3.6. Suicidal ideation and behavior risk monitoring

Participants with HIV infection occasionally may present with symptoms of depression and/or suicidality (suicidal ideation or behavior). In addition, there have been some reports of depression, suicidal ideation and behavior (particularly in patients with a pre-existing history of depression or psychiatric illness) in some patients being treated with INIs, including DTG. Therefore, it is appropriate to monitor participants for suicidality before and during treatment.

Participants should be monitored appropriately and observed closely for suicidal ideation and behavior or any other unusual changes in behavior. It is recommended that the investigator consider mental health consultation or referral for participants who experience signs of suicidal ideation or behavior. Participants presenting with new onset/treatment emergent depression should be advised to contact the investigator immediately if symptoms of severe acute depression (including suicidal ideation/attempts) develop, because medical intervention and discontinuation of the study medication may be required.

Assessment of treatment-emergent suicidality will be monitored during this study using the electronic version of the Columbia Suicidality Severity Rating Scale (eC-SSRS). The definitions of behavioral suicidal events used in this scale are based on those used in the Columbia Suicide History Form [Posner, 2007]. Questions are asked on suicidal behavior, suicidal ideation, and intensity of ideation. Screening visit questions will be in relation to lifetime experiences and current experiences (within the past 2 months); all subsequent questioning is in relation to the last assessment. The eC-SSRS questionnaire is to be administered by a clinician at the timepoints in the SoA (Section 1.3). The eC-SSRS will be conducted electronically by computer.

Additionally, the investigator will collect information using the Possible Suicidality-Related AE (PSRAE) eCRF form in addition to the AE (non-serious or SAE) eCRF form on any participant that experiences a possible suicidality-related AE while participating in this study. This may include, but is not limited to, an event that involves suicidal ideation, a preparatory act toward imminent suicidal behavior, a suicide attempt, or a completed suicide. The investigator will exercise his or her medical and scientific judgment in deciding whether an event is possibly suicide-related. PSRAE forms should be completed and reported to VH/GSK within 1 week of the investigator diagnosing a possible suicidality-related AE.

8.3.7. Study Pausing Rules

Participant safety will be continuously monitored by the VH medical monitor and the GSK safety lead. Pertinent findings and conclusions are shared with the product's SRT for review of the overall benefit-risk profile of the product. The sponsor's governance

group, the ViiV Safety and Labelling Committee (VSLC) will review data and the team's recommendation when any pausing/stopping rules are met. The VSLC will govern whether enrollment may be resumed/modified, a given treatment arm will be stopped, or the study stopped.

The following study pausing criteria would be applied per compound:

- Any SAE, regardless of its severity, that is considered to be clinically significant and reasonably attributable to dosing with VH4004280 or VH4011499, in the opinion of the investigator or the Sponsor.
- Any Grade 3 or higher rash or Grade 2 rash with evidence of systemic involvement that the investigator considers reasonably attributable to VH4004280 or VH4011499.
- Any Grade 4 AE or laboratory abnormalities (with the exception of an asymptomatic Grade 4 lipid abnormalities or CPK increase) that the investigator considers reasonably attributable to VH4004280 or VH4011499.
- Any participant meeting liver stopping criteria that the investigator considers reasonably attributable to VH4004280 or VH4011499.
- Any participant meeting QTc stopping criteria that the investigator considers reasonably attributable to VH4004280 or VH4011499.

8.4. Adverse Events (AEs) and serious adverse events (SAEs)

For definitions relating to safety information see Section [10.3](#).

The investigator and any qualified designees are responsible for detecting, documenting, and recording events that meet the definition of an AE or SAE and remain responsible for following up AEs that are serious, considered related to the study intervention or study procedures, or that caused the participant to discontinue the study (Section [6.9](#)). This includes events reported by the participant (or, when appropriate, by a caregiver, surrogate, or the participant's legally authorized representative).

The method of recording, evaluating, and assessing causality of AEs and SAEs and the procedures for completing and transmitting SAE reports are provided in Section [10.3](#).

